English

Groups to be recruited will include:

Patients

Which if any of the following vulnerable populations will be recruited as subjects?

Vulnerable populations require special protections. How will you obtain informed consent, protect subject confidentiality, and prevent undue coercion?

Pregnant woman/fetus

Will pregnant women and/or fetuses (as described in 45 CFR 46 Subpart B) be enrolled in the research?

No

Neonates

Will neonates of uncertain viability or nonviable neonates (as described in 45 CFR 46 Subpart B) be enrolled in the research?

No

Children

Will children be enrolled in the research?

No

Design/Procedure**Design**

Select one category that most adequately describes your research:

c) Pilot

Discuss the research design including but not limited to such issues as: probability of group assignment, potential for subject to be randomized to placebo group, use of control subjects, etc.

This study is a prospective interventional study, which involves use of existing and prospectively collected data. This pilot study will be conducted at Baylor College of Medicine examining the feasibility, safety, acceptability, and preliminary efficacy of home-based exercise on frailty parameters and Short Physical Performance Battery score in patients with varying levels of kidney function. We plan to accrue up to 20 adult patients with chronic kidney disease. The effects of exercise on health-related quality of life, physical activity, and adverse outcomes including hospitalizations and death, will also be explored.

Inclusion Criteria:

1. Age 18 years or older
2. Ability to consent to research
3. Chronic kidney disease (stages 1-5)
4. A Short Physical Performance Battery score ≤ 10 and/or considered frail or pre-frail according to the Fried Frailty Phenotype

Exclusion Criteria:

1. Younger than 18 years
2. Patients being evaluated for combined organ transplantation
3. Significant comorbidities that limit rehabilitation potential including pulmonary disease requiring continuous oxygen supplementation, active angina, critical aortic sclerosis, decompensated heart failure, or known ventricular arrhythmia.
4. An Short Physical Performance Battery score >10 or not considered frail or pre-frail by the Fried Frailty Phenotype
5. Non-English speaker without availability of adequate interpreter services (safety concern)
6. Failure to pass submaximal exercise test in patients not approved for kidney transplantation at our center

Procedure

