Screening and Recruitment:

Potential participants will be identified from dialysis units, nephrology clinics, primary care clinics, or kidney transplant clinics at Baylor College of Medicine clinic. If the study team is unable to reach the patient after three attempts involving phone calls and/or portal messages, an Institutional Review Board-approved contact letter may be sent up to two times. Patients who express interest in the study will go through the informed consent process with a member of the study team, and patients wishing to participate in the study will complete written consent. If patients have not had frailty and Short Physical Performance Battery testing within the two weeks prior to consent, the study team member will perform frailty and Short Physical Performance Battery testing at baseline in a supervised setting. Patients who are not frail or pre-frail and have a Short Physical Performance Battery score > 10 will be ineligible for study participation. Patients with stage 1-5 chronic kidney disease who are not currently approved for kidney transplant at our center will undergo a submaximal exercise test to rule out any significant, undiagnosed cardiopulmonary disease if they meet one or more of the following criteria: 1) diabetes, 2) age > 59, 3) prior coronary artery disease defined as history of myocardial infarction, coronary artery stenting, or coronary artery bypass grafting, or 4) current smoking. During the initial study visit, consenting patients will be provided with a pedal exerciser, resistance bands, and exercise pamphlets (Mayo Clinic Patient Education Pulmonary Rehabilitation: Exercise Program, Exercise Program Guidelines, Exercises for the Legs). Participants will be given the option of having the pedal exerciser mailed to their home.

Exercise Intervention:

Participants will be asked to complete an 8-week home-based exercise program with a focus on the core components of physical activity counseling and exercise training according to guidelines from the American Heart Association and the American Association of Cardiovascular and Pulmonary Rehabilitation (Balady GJ Circulation 2007). During the program, participants will receive weekly semi-scripted phone calls from an exercise physiologist from the Mayo Clinic Cardiac Rehabilitation program. During the baseline phone call, the exercise physiologist will assess the patients current level of physical activity; discuss warm-up, cool-

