down, and flexibility exercises; review the Borg Rating of Perceived Exertion (RPE); set goals with the patient; and answer any questions they might have. The exercise physiologist will then document in the electronic medical record any warning symptoms the participant experienced during physical activity or exercise; recent hospitalizations, important medical appointments, urgent care, or emergency department visits; goals set during phone call; an individualized exercise prescription. Study personnel will then send the individualized exercise prescription to the participant via mail, portal, or email. Recommended aerobic exercises will include arm and/or leg ergometry using a pedal exerciser. Recommended resistance training will include resistance bands. Patients will be encouraged to obtain at least 30 minutes of moderate-intensity physical activity at least five days per week. Gradual increases in the volume of physical activity will be recommended over time. Participants on dialysis will be advised not to exercise after in-center hemodialysis on dialysis days (if applicable). Participants will be asked to log information regarding their exercise sessions on paper, including type, duration, and Borg RPE scale.

During the subsequent weekly phone calls, the exercise physiologist will inquire about any interim symptoms or events, answer any questions regarding the exercise program, review goals set during the previous phone call and what the patient has done to work toward those goals, and set new goals if applicable. During each weekly phone call, the exercise physiologist will review and record information from the patients exercise log and enter it into the patients electronic medical record. Information entered by exercise physiologists into the electronic medical record will also be entered into REDCap by study personnel.

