A Data Transfer Agreement will be obtained between Mayo Clinic and Baylor College of Medicine so that a limited data set involving subjects from Mayo Clinic can be accessed from Baylor College of Medicine. Mayo Clinic will share the data with Baylor using encrypted email and/or Microsoft Simple Share. The limited dataset that will be shared will include demographics, dates of participation in the exercise intervention, information about the exercise intervention (i.e. duration of study phone calls, participant exercise log), study outcome data (including data from frailty assessments, body composition assessments, accelerometers, and questionnaires), and medical/laboratory information abstracted from the medical record.

Sample Size/Data Analysis

Sample Size

How many subjects (or specimens, or charts) will be used in this study?

Local: 20 Worldwide: 20

Please indicate why you chose the sample size proposed:

This is a pilot study so it doesn't require sample size calculations. However, we chose our recruitment target based on a prior study examining the impact of exercise on frailty parameters which was able to show significant differences with a similar number of study participants.

Data Analysis

Provide a description of your plan for data analysis. State the types of comparisons you plan (e.g. comparison of means, comparison of proportions, regressions, analysis of variance). Which is the PRIMARY comparison/analysis? How will the analyses proposed relate to the primary purposes of your study?

Categorical variables will be summarized as counts and percentages with continuous variables summarized via medians and interquartile ranges. Pre- and post- comparisons will be made using paired, one-sample Wilcoxon signed rank tests for continuous variables and chi-square tests for categorical variables. Differences between groups will be assessed using two-sample Wilcoxon tests for continuous variables and Fisher's exact tests for categorical variables. P-values less than 0.05 will be considered statistically significant. We will make no adjustments in the p-value for multiple hypothesis testing.

Potential Risks/Discomforts

Describe and assess any potential risks/discomforts; (physical, psychological, social, legal, or other) and assess the likelihood and seriousness of such risks:

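### In a single-group before/after design, entry rules that admit patients in other supervised rehabilitation or recovering from a hospital stay let that change count as programme effect

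*Combined protocol and SAP*

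**What the plan says.** - **Design.** Design/Procedure describes "This study is a prospective interventional study, which involves use of existing and prospectively collected data". The form asks about control subjects and the answer describes none. The Exercise Intervention section applies to everyone: "Participants will be asked to complete an 8-week home-based exercise program".
- **Size.** "We plan to accrue up to 20 adult patients with chronic kidney disease". Under Sample Size: "This is a pilot study so it doesn't require sample size calculations". No effect size, SD, power or dropout rate is given.
- **Exclusions.** There are six: age, evaluation for combined organ transplantation, comorbidity, good physical function, language, and a failed submaximal exercise test. The comorbidity item begins "Significant comorbidities that limit rehabilitation potential including pulmonary disease requiring continuous oxygen supplementation, active angina" and adds three more cardiac conditions. None of the six mentions other rehabilitation or physical therapy, time since a hospital stay, or a recent or expected transplant or dialysis start.
- **Recruitment.** "Potential participants will be identified from dialysis units, nephrology clinics, primary care clinics, or kidney transplant clinics".
- **Data captured.** At the baseline call the exercise physiologist documents "recent hospitalizations, important medical appointments, urgent care, or emergency department visits". Interim symptoms and events are asked about weekly, and what the physiologist enters is copied to REDCap. Time on dialysis and previous kidney transplant are collected at baseline. Other supervised rehabilitation is not a named item.
- **Analysis.** "Pre- and post- comparisons will be made using paired, one-sample Wilcoxon signed rank tests" for continuous variables, at 0.05 without multiplicity adjustment. The Data Analysis section does not say how hospital stays or interim events are used.

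**The concern.** With no comparison group, anything that moves function between the two tests enters the paired difference and is read as the effect of the programme. Two sources are foreseeable and tend to favour the programme.

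- **Other supervised exercise.** Background Information reports that 21 patients with advanced chronic kidney disease attended supervised sessions twice a week for 8 weeks, and that this was associated with improved frailty parameters and SPPB. Outcome and duration are the same as here. On the sponsor's own evidence, a participant attending such a programme has another reason to improve.
- **Recovery after a hospital stay.** A patient tested soon after discharge may score low enough to qualify and then improve over 8 weeks without any programme.

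Both are real clinical change, so more careful measurement would not remove them. At stake is the reading of the only efficacy result, from at most 20 people, in a study whose Purpose and Objectives section sets out to determine whether the intervention is effective.

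**Working it through.** **1. The plan's own figure.** The sample size of 20 cannot be reproduced, because no effect size, SD or power is stated. For scale, a paired comparison of 20 at two-sided 0.05 (the plan does not state sidedness) has 80% power for a mean change of (1.960 + 0.842)/√20 = 0.63 SD. This is a normal approximation; by the t distribution it is 0.66 SD.

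**2. Is there a control elsewhere?** Data Analysis mentions differences between groups but defines no groups. The data-transfer paragraph describes a limited data set from a second institution that includes dates and details of the exercise intervention, so it does not describe an untreated comparison group either.

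**3. How far can a few such patients move the test?** Assumptions, none from the documents except n = 20 and alpha = 0.05:
- true programme effect zero
- SPPB change normal with mean 0 and SD 1.2, rounded to whole points, ignoring any ceiling on the score
- k of the 20 shifted by +2 points for another reason
- signed-rank test, two-sided 0.05, counting only results in favour of the programme

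Shift in mean change = 2k/20 points.

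| k of 20 | Mean shift (points) | Chance of false significant benefit |
|---|---|---|
| 0 | 0 | about 2% |
| 1 | 0.10 | about 4% |
| 2 | 0.20 | about 7% |
| 3 | 0.30 | about 11% |
| 4 | 0.40 | about 15% |

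With 4,000 simulated trials the standard error at 15% is √(0.15 × 0.85/4000) = 0.6 percentage points. Repeat runs put three patients at 10% to 11% and four at 15% to 17%. If four improve by 3 points the figure is 22% to 24%.

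**4. Same question in SD units** (normal changes, 10,000 trials):
- 2 of 20 improving by 1 to 2 SD: 5% to 7%
- 4 of 20: 9% to 18%
- 6 of 20: 18% to 37%

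**5. Size against a detectable effect.** With SD 1.2, 0.63 SD is 0.63 × 1.2 = 0.75 points. One patient shifts the mean by 0.10/0.75 = 13% of that, and four by 0.40/0.75 = 53%.

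**6. Shifts in both directions** (same model as step 3, shifts of 2 points):
- two up, one down: about 3%
- three up, one down: about 4%
- two up, two down: about 1%

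The inflation largely disappears when some of the other changes are losses.

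**The case against.** **It is a pilot.** The Design section speaks of feasibility, safety, acceptability and preliminary efficacy in a deliberately broad population. This stands as a reason not to ask for a control arm: 10 v 10 would have 29% power for a 0.63 SD difference in change. It does not excuse leaving avoidable rival causes in the paired result, because Purpose and Objectives is worded as a test of effectiveness and significance is declared at 0.05.

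**The number of such patients is unknown.** This stands. A reader might infer that a few patients can decide the result. The working does not support that for one or two, who take the false-benefit rate only to 4% and 7%. Even with four, roughly 85% of null trials show no significant benefit.

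**Transplant or dialysis start.** Because recruitment includes transplant clinics, and patients already approved for transplant are mentioned, a reader might infer that such events between the tests also inflate the effect. The documents do not support this. They give no waiting time, the Background stresses the scarcity of organs, and approved patients appear only in connection with the submaximal exercise test. Either event could lower function as well as raise it.

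**The data are already collected.** Largely true for hospital use and interim events. The gap is in eligibility, in one unnamed item (other supervised exercise), in explicit recording of transplant and dialysis start, and in the analysis.

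**The comorbidity exclusion is open-ended.** It removes some acutely ill patients, for example those with active angina or decompensated heart failure. It sets no interval after a hospital stay and does not address other rehabilitation.

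**Conclusion.** The point holds in a limited form. As written, the plan can enrol patients in other supervised rehabilitation or recovering from a hospital stay, and it credits their change to the programme. The bias is modest with one or two such patients and material from about three or four of 20 (11% and 15% against a base of about 2%). These figures rest on an assumed SD of 1.2 points, an assumed improvement of 2 points, and counts that the documents do not give.

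Transplant or dialysis start between the tests is a source of noise of unknown direction, not a demonstrated upward bias. A reader might also infer that function measured after such an event should be dropped from the main result. That does not follow: it would select on events after baseline, change the question answered and lose pairs from a small sample.

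**What to change.** 1. Add one exclusion: current supervised rehabilitation or physical therapy. This fits the stated rationale, which is patients unable to attend a center-based program.
2. Add other supervised exercise, transplant and dialysis start as named items on the weekly calls. Recent hospitalisations and interim events are already captured.
3. Keep all participants in the main before/after analysis.
4. Pre-specify one sensitivity analysis that repeats the comparison without participants who had a recent hospitalisation before baseline, or a transplant, dialysis start or other supervised exercise between the tests. Define recent in advance; the documents give no basis for a particular interval.

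**Cost.** One exclusion line, three recorded items and one extra analysis. A few patients become ineligible. The change does not supply a control arm, and it does not remove regression to the mean from selecting on low SPPB or frailty, so the report should still describe the result as an uncontrolled change.

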Participants will be instructed to stop exercising and sit down and rest if they develop any of the following signs: chest tightness, pressure, or pain; severe shortness of breath; light-headedness or dizziness; stomach pain; upset stomach, throwing up or a headache; pulse rate that is not normal for them; extreme fatigue; profuse sweating. They will be advised to seek emergency care (call 911) immediately for chest tightness, pressure, or pain in the chest or severe shortness of breath that does not go away within 3 to 5 minutes. Home-based exercise will be stopped if the study team feels it is no longer safe for the participant to continue exercise. If a participant experiences any of the above symptoms during or after exercising, the principal investigators will be notified. If the principal investigators determine it is no longer safe for the participant to continue the exercise program following discomfort, injury, or a medical emergency during an exercise session, the participant will be withdrawn from the study. Reasons for participant withdrawal will be recorded.

Study measures:

Participants will complete the following Short Physical Performance Battery testing and other study measures at baseline and after completion of the exercise program:

1. Fried Frailty Phenotype: The Fried Frailty Phenotype consists of a gait speed test, a grip strength test, and self-reported measures of physical activity, weight loss, and exhaustion. a. Gait speed test: The time required for the participant to walk a distance of 15 feet at a self-

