We expect the occurrence of adverse events to be rare. All AEs will be reported immediately to the principal investigators and properly documented. Serious Adverse Events (SAEs), Unanticipated Problems Involving Risks to Subjects or Others (UPIRTSOs), and any major protocol violations will be reported to the IRB within 5 working days of the event. AEs and any minor protocol violations will be reported at the time of the continuing review. An explanation of the event and how the event was handled will be submitted with each report. The number of complaints and the number of study participants who withdrew from the study will be reported at each continuing review along with explanations for each complaint and for each withdrawal.

There is a minimal risk of injury or discomfort during the exercise sessions, and participants may be unwilling to answer certain questions within the questionnaires. The potential risks of the study are estimated to be equivalent to daily activities.

Potential Benefits

Describe potential benefit(s) to be gained by the individual subject as a result of participating in the planned work.

There are no immediate benefits to the participants from this study. The potential benefits of this study include improved physical function for the participant.

Describe potential benefit(s) to society of the planned work.

The investigators hope is to identify whether our hypothesis of a home-based exercise program will be feasible, safe, acceptable to patients, and improve frailty parameters and Short Physical Performance Battery scores in patients with varying levels of kidney functions. And if the findings of the study support hypothesis, a home-based exercise program could be

implemented prior to kidney transplantation with the ultimate goal of improving health-related quality of life and transplant outcomes in kidney transplant candidates in future.

Do anticipated benefits outweigh potential risks? Discuss the risk-to-benefit ratio.

The expected benefits of developing a feasible and effective exercise intervention in patients with decreased physical function outweigh the possible risks.

Consent Procedures

Waiver of Consent

Will any portion of this research require a waiver of consent and authorization?

NA

Waiver of requirement for written documentation of Consent

Will this research require a waiver of the requirement for written documentation of informed consent?

NA

Consent Procedures

Who will recruit subjects for this study?

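### After a stop symptom at home, the protocol text sets no hold on the next session until the principal investigators have reviewed it; add a limited hold with same- or next-day reporting

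*Combined protocol and SAP*

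**What the plan says.** The combined protocol and SAP covers symptoms during home exercise in two places.

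**Procedure, Exercise Intervention.** The programme's length is given as: "Participants will be asked to complete an 8-week home-based exercise program". Contact during it is scheduled once a week: "participants will receive weekly semi-scripted phone calls from an exercise physiologist from the Mayo Clinic Cardiac Rehabilitation program". Symptoms are asked about then: "During the subsequent weekly phone calls, the exercise physiologist will inquire about any interim symptoms or events". Participants also "log information regarding their exercise sessions on paper, including type, duration, and Borg RPE scale", and the physiologist goes through this log at each call.

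For stop symptoms, the instruction begins: "Participants will be instructed to stop exercising and sit down and rest if they develop any of the following signs". The list covers chest symptoms, severe breathlessness, light-headedness or dizziness, stomach and headache symptoms, an abnormal pulse, extreme fatigue and profuse sweating. Participants are to call 911 for chest symptoms and for severe breathlessness, with a 3 to 5 minute qualifier attached. The team then acts: "If a participant experiences any of the above symptoms during or after exercising, the principal investigators will be notified". The next step is conditional: "If the principal investigators determine it is no longer safe for the participant to continue the exercise program" after discomfort, injury or an emergency during a session, the participant is withdrawn. The study team may also stop the exercise on its own judgement.

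**Potential Risks/Discomforts.** A general rule applies: "All AEs will be reported immediately to the principal investigators and properly documented".

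**The concern.** The safeguard after a stop symptom is a decision by the principal investigators, and they can decide only once they know. The text says what the participant does in the moment and what the investigators do once informed. It does not say what the participant does between the two. No sentence tells the participant to leave out the next session, and the outcomes described are to continue, to stop or to be withdrawn. A temporary pause pending review is not among them.

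The gap matters most for symptoms that pass. The 911 advice covers emergencies without waiting for the team. It does not cover a spell of dizziness or an abnormal pulse that settles with rest. Someone following the text could exercise again the next day. These participants are frail or pre-frail, or score 10 or below on the Short Physical Performance Battery, and they exercise alone. Safety is one of the aims named under Design.

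**Working it through.** The plan states no reporting time in days, so there is no figure of its own to reproduce. The size follows from simple counting.

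**Inputs from the Exercise Intervention section**
- Scheduled contact: weekly, so 7 days between calls.
- Encouraged activity: at least five days per week, for 8 weeks.

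**Assumptions**
- One session per active day.
- No contact with the team between calls.
- The participant resumes once the symptom has settled.

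**Step 1: delay until the team knows.** A symptom just after one call is first asked about at the next, so the delay is at most 7 days. If onset is evenly spread over the week, the mean is about 7 / 2 = 3.5 days.

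**Step 2: further sessions in that time.** With n sessions between two calls and the symptom at session k, n − k remain.
- n = 5: 4, 3, 2, 1 or 0 remain. The maximum is 5 − 1 = 4. If each session is equally likely, the mean is (4 + 3 + 2 + 1 + 0) / 5 = 2.
- n = 7 (daily, which the encouraged minimum allows): the maximum is 7 − 1 = 6.
- n = 3 (assumed lower adherence): the maximum is 3 − 1 = 2, and the mean is (2 + 1 + 0) / 3 = 1.

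**Step 3: do other provisions shorten this?**
- Notification of the investigators and immediate adverse event reporting both start when someone on the team knows. Neither gives the participant a step to take.
- The paper log is reviewed at the weekly call, so a symptom written there would not reach the team sooner.
- The submaximal exercise test (Screening and Recruitment) lowers the underlying risk. It applies only to patients not approved for transplant at the center who have at least one listed risk factor, and it does not bear on reporting.

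**Step 4: cost of a hold.** The encouraged dose is 8 × 5 = 40 sessions, or 5 / 7 of a session per day. A hold of 1 to 3 days (assumption) loses 1 × 5/7 = 0.7 to 3 × 5/7 = 2.1 sessions. As a share of the dose, that is 0.71 / 40 = 1.8% to 2.14 / 40 = 5.4% for each hold.

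The documents give no symptom rate, so neither the expected number of exposed sessions nor the number of holds can be estimated.

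**The case against.** The strongest objection is that much of this may already be covered. Consent and contact pages are not in the file, nor are the exercise pamphlets and the call script. Any of them could tell participants to ring the team. A reader might infer that participants are never told to report symptoms between calls. The documents do not support that, because the places where such an instruction would usually sit cannot be seen. This part of the objection stands, and the reporting step is therefore something to confirm.

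Second, the protocol makes the symptom itself the trigger for notification and requires immediate reporting of adverse events. It nowhere says that the weekly call is the only route. This also stands: the 7-day figure is an upper bound that assumes no unscheduled contact. A reader might go further and infer that serious events would reach the IRB late. Nothing in the text shows a breach of that deadline.

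Third, a participant with chest symptoms should already have called 911. That is largely right, although the 3 to 5 minute qualifier can be read as applying to chest symptoms too. The case for a hold rests more securely on settled dizziness or an abnormal pulse.

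Fourth, this is a 20-person pilot classed as minimal risk, with cardiac and pulmonary exclusions, and no analysis changes. That limits the weight of the point but does not remove it. Even if participants are told to report, no visible text pauses exercise until the investigators have decided.

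**Conclusion.** The point holds as a cheap improvement to the safety procedure. The protocol relies on investigator review after a stop symptom but, in the available text, sets no hold until that review takes place. The only described route to the team is the weekly call. If there is no unscheduled contact and the participant resumes, up to 4 further sessions at five per week, or up to 6 if daily, could take place over at most 7 days before the investigators know. The averages depend on evenly spread onset and are illustrative.

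Confidence is medium, because the participant materials cannot be checked and the symptom frequency is unknown. Once the team knows, the plan's provisions are adequate.

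A reader might also infer that prompt reporting alone would cap exposure at one further session. It would not: a portal message sent at a weekend may wait to be read. The hold gives the protection, because it starts at the symptom and does not depend on when the message is seen.

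**What to change.** In the stop-symptom text of the Exercise Intervention section:

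1. **Hold.** Tell participants not to resume exercise after chest symptoms, severe breathlessness, light-headedness or dizziness, an abnormal pulse, extreme fatigue, profuse sweating, an injury or an emergency visit until they have contacted the study team and been cleared by the principal investigators.
2. **Reporting.** Have them report these the same or next day by phone or portal. If the consent form or pamphlets already say so, confirm it and refer to it.
3. **Milder symptoms.** Leave headache, upset stomach, stomach pain or vomiting alone to the weekly call unless they persist.
4. **Cross-reference.** State that listed symptoms heard by the physiologist fall under the immediate reporting rule in Potential Risks/Discomforts. The caller works at another institution and records calls in the medical record, and the section does not say who alerts the investigators.

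If the reporting instruction already exists, only the hold, its exceptions and the cross-reference are new. No visits are added. The cost is a few extra calls and some paused sessions, at the per-hold loss worked out above. The division between hold and no-hold symptoms is a clinical judgement for the investigators to confirm.
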